9.5 Follow-up Evaluations

Follow-up assessments will occur at months 12 and 24 from baseline +/- 3 months. Study patients will be reminded of their follow up visit. The following will occur at all follow-up visits:

- Two weeks prior to the appointment (-21 to -7 days) Orthodontic rubber spacers will be inserted next to the iconized lesions to separate the proximal space for better visualization.
- Radiograph exam of study lesion
- Visual exam of study lesion
- SFE laser optical device imaging of study lesion

Results are documented in CRF (Appendix A1).

If study lesions are noted to be progressing at any point the study clinician will refer the participant for standard-of-care treatment to the CPD Resident Clinic. Progression is defined as lesion changes

from E2 to D category according to DMG's criteria. The study participant will no longer participate in the study at this point.

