11.3 Evaluation Strategy

The bitewing radiographs will be examined and assessed by evaluators for positive, none or negative change in size and density.

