11.4 Statistical Analysis

11.4.1 Descriptive Statistics

Descriptive statistics (means, standard deviations, counts, and percentages) will be calculated for all variables. A Chi-square test of association will be performed to evaluate if there is a significant difference in caries arrest by treatment group at a significance level of 0.05. Additional Chi-square tests of association will be performed to determine if there is a significant association with the secondary outcomes by treatment group.

11.4.2 **Blinding**

Each subject enrolled into this study will be assigned a unique identifying code number. Every effort will be made to maintain the confidentiality of each study subject's identity. No presentation or publication of the study data will identify any study subject.

11.4.3 **Evaluation of Records**

SFE laser optical device image diagnoses from each time point will be compared to diagnoses from radiograph and visual exams from chart review from the same visit.

- For radiograph and visual exams: Assessments of caries lesions per standard of care will be abstracted from the electronic dental record system (Axium) and recorded on CRF.
- For SFE laser optical device image: Recordings from the device will be used to assess caries lesions and recorded on CRF.

11.4.4 **Missing Data**

Missing data due to dropouts have been accounted for in adjusted sample size. The missing data will be at random. Data of dropouts will be assigned as "last observation carried forward".

11.4.5 **Statistical Software**

STATA Data Analysis and Statistical Software will be utilized to perform data analysis.

12 Method of Reporting

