The primary endpoint in this study is the proportion of study lesions that have progressed, whereby a difference in caries progression of 40% after 2 years between resin infiltrated teeth and control will be assumed. This difference is based on a previous infiltration study by Ekstrand et al. [45] who reported a 1-year difference in caries progression in primary teeth of 39% (resin infiltration (23%) vs. control (62%)), which was furthermore comparable to results obtained in young adults. Martignon et al [42] for example reported a difference in caries progression in permanent teeth of 37% and 38% after 1 and 2 years respectively; and Meyer-Lueckel et al. of 30% after 18 months.

Based on an assumed difference in caries progression of 40% between resin infiltrated teeth and control, with alfa = 0.05 and a power of 80% the calculated sample size (t-test; matched pairs) would be 42 lesions to find significant differences. To allow for a potentially attrition rate of at least 20% over a period of 2 years a total of 50 lesions will be included.

Statistical Analysis

All evaluations are performed by one trained examiner. The primary outcome is proportion of study lesions that progressed after 2 years as measured via dental examination and pairwise comparison of radiographs. Differences between groups will be tested using Fisher's exact test.

Secondary outcomes are the proportion of study lesions that progressed after 1 year as well as change in categorical lesion depth (progression to next depth category lesion; E1->E2->D1->D2->filling) after 1 and 2 years as measured by pairwise comparison of radiographs. In addition, the change in categorical lesion depth will be determined via SFE laser optical device imaging after 1 and 2 years and compared to the change in categorical lesion depth as measured by pairwise comparison of radiographs. Differences in categorical lesion depth will be analyzed with Chi-square tests with 95% confidence interval (95% CI) and P = .05.

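### The SAP's primary outcome, lesions that progressed by 2 years, has no depth threshold; the protocol and SAP disagree on E1-to-E2 lesions, and the examination part appears to be made under arm-dependent conditions

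*Combined protocol and SAP*

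**What the plan says.** **Primary outcome.** The SAP (Statistical Analysis) states: "The primary outcome is proportion of study lesions that progressed after 2 years as measured via dental examination and pairwise comparison of radiographs". No category change is attached to it. A step rule, "progression to next depth category lesion; E1->E2->D1->D2->filling", appears in the next paragraph, but only for a secondary outcome.

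**Protocol definition.** Section 9.5 says "Progression is defined as lesion changes" "from E2 to D category according to" the DMG criteria. The participant is then referred for standard care, and "The study participant will no longer participate in the study at this point".

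**Withdrawal table.** Table 14.1.2 (section 14.2) scores a lesion as progressed and as a failure when it reaches D2 or D3, or when the tooth shows pulpitis. D1 has no row.

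**Radiographic rating.** Section 11.3: "The bitewing radiographs will be examined and assessed by evaluators for positive, none or negative change in size and density". Nothing links this rating to progression.

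**Source and assessor.** Specific Aim I (6.2.1) is caries arrest on bitewings alone. The SAP adds a dental examination. Section 11.3 has evaluators in the plural, while the SAP says "All evaluations are performed by one trained examiner".

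**Conditions at follow-up.** Section 9.5 places spacers beside the iconized lesions before the 12- and 24-month visits, and Table 8.2 labels the spacer row as treatment group. Before baseline, section 9.1 gives spacers to both groups. Sections 6.4 and 11.1 call the trial blinded. Section 11.4.2, headed Blinding, covers ID codes and confidentiality.

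**The concern.** A single primary test needs one event definition. Here the SAP names none. The protocol's only explicit definition and the SAP's only step rule disagree on a change that enrolled lesions can undergo. An analyst who follows the documents can reach different event counts from the same radiographs, and nothing prevents the rule from being settled after the data are seen. With 50 lesions, reclassifying a few could change the result.

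The second problem is how the outcome is observed. The examination is part of the SAP's primary. If teeth are separated for better viewing mainly or only in the Icon arm, the examiner sees the two arms under different conditions and can tell which arm a lesion belongs to. A coded radiographic reading would limit this, but the visible text describes no such procedure.

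**Working it through.** **1. The rules side by side.** Section 7.2.1 enrols E1 and E2 lesions.

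| Change from baseline | Section 9.5 | SAP step rule (secondary outcome) | Table 14.1.2 |
|---|---|---|---|
| E1 to E2 | Not progressed | Progressed | Silent |
| E2 to D1 | Progressed; participant leaves | Progressed | No row |
| E2 to D2 or deeper | Progressed; participant leaves | Progressed | Progressed and failure |
| Pulpitis without depth change | Silent | Not covered | Progressed and failure |

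There are two hard conflicts: the E1-to-E2 row, and the exit thresholds (any D in 9.5, D2/D3 in Table 14.1.2). A participant who leaves at D1 is no longer followed to the depth that the table scores.

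**2. The plan's own sample size.** The SAP gives 42 lesions for a 40-point difference, alpha 0.05 and 80% power. It names a matched-pairs t-test but gives no SD or correlation. The unpooled two-proportion formula reaches 42 with 63% v 23% (the cited 23% plus 40 points):

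n per arm = (1.960 + 0.842)² × [p₁(1−p₁) + p₂(1−p₂)] / d²
= 7.849 × (0.2331 + 0.1771) / 0.16 = 20.1, so 21 per arm and 42 in total.

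A paired t-test on 0/1 outcomes at the same rates, with an assumed within-pair correlation of 0.1, also needs 21 pairs. For attrition, 42 × 1.2 = 50.4, close to the 50 enrolled; 50 × 0.8 = 40 leaves 20 per arm. The figure depends on one pair of progression rates, and the plan does not say which threshold those rates refer to.

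**3. What the choice of rule does (illustration only).** Assumptions:
- Rates of 62% control and 22% Icon by next category. The first is the cited control rate; the second is that rate less 40 points.
- Lesions are independent, although two per child are allowed.
- The planned Fisher's exact test is two-sided at 0.05.
- A share s of progressions is E1 to E2. The documents do not give this share.

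E2-to-D rate = next-category rate × (1 − s), with the same s in both arms:

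| s | Control | Icon | Power, 25/arm | Power, 20/arm |
|---|---|---|---|---|
| 0 | 62% | 22% | 79% | 63% |
| 25% | 0.62 × 0.75 = 46.5% | 0.22 × 0.75 = 16.5% | 52% | 43% |
| 50% | 0.62 × 0.50 = 31% | 0.22 × 0.50 = 11% | 29% | 23% |

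With unequal shares, power moves either way. At 25 per arm, 50% of control and 25% of Icon progressions gives 31% v 16.5% and 13.5%. Shares of 25% and 75% give 46.5% v 5.5% and 91%.

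**The case against.** The best reply is that the passages serve different purposes. Section 9.5 is a referral-and-exit rule, Table 14.1.2 a withdrawal table, and 11.3 a rating scale. This stands in part, and it rules out several stronger readings that a reader might infer.

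- *Four rival definitions.* The table makes D2/D3 or pulpitis sufficient for progressed, not necessary, so it does not say that an E1-to-E2 or D1 lesion has not progressed. Section 11.3 never equates a negative rating with progression.
- *The primary comes from chart abstraction.* Section 11.4.3 says "Assessments of caries lesions per standard of care will be abstracted from the electronic dental record system (Axium) and recorded on CRF", but under a sentence on comparing SFE diagnoses with the other examinations. It is not stated as the source for Aim I.
- *A second lesion in an exiting child has no rule.* The general last-observation-carried-forward rule in 11.4.4 plausibly covers it. What is missing is a statement that such a child counts as a dropout.
- *Externally treated lesions are mishandled.* Table 14.1.2 gives an explicit carry-forward rule. Filling is a step only on the secondary scale. Recoding these lesions as progressed would be a preference.
- *Assessment is shown to be unmasked, by the person who treated.* The text never says so. Section 8.2 gives both roles to a study clinician, not necessarily one person, and 18.2 provides for un-blinding. Neither the research-team section (21.1) nor the CRF is in the text available here. Section 9.5 does not say that control lesions get no spacers.

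None of this supplies the missing threshold or reconciles 9.5 with the SAP's step rule.

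**Conclusion.** The point holds and needs correcting before outcome data are seen. It rests on the text: the SAP's primary has no threshold, 9.5 and the SAP's step rule disagree on E1-to-E2 lesions, 9.5 and Table 14.1.2 disagree on the depth that ends participation, and the examination has no combining rule.

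The observation problem is a reasonable inference from 9.5 and Table 8.2, not a stated fact: the examination part of the primary appears to be made under conditions that differ by arm and reveal it. A reader might infer that this favours Icon. The documents do not support a direction. Separation could expose more change at Icon lesions, and an assessor who knows the arm could err either way.

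Under the assumed 62% v 22%, independent lesions and equal E1-to-E2 shares of 25% to 50%, moving from next category to E2-to-D takes power from 79% to between 52% and 29% at 25 per arm, and from 63% to between 43% and 23% at 20 per arm. The wider 13.5% to 91% range needs shares that differ by arm, so it should not be read as the effect of the threshold alone. The figures show only that the result depends on the rule.

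**What to change.** Before outcome data are seen, state one primary endpoint in 6.2.1, 9.5, 11.3, 11.4.2, 14.2 and the SAP. One choice that fits Aim I and the SAP's scale is at least one radiographic category deeper than baseline by 24 months. It would be taken from the SAP's pairwise bitewing reading, on coded images with arm and visit notes withheld. Other consistent choices exist. With this one:

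- Report E2-to-D as a sensitivity analysis and the dental examination as secondary.
- Count a lesion that triggers the 9.5 exit as progressed. State that the existing carry-forward rule applies to a non-progressed second lesion of that child.
- Keep the written carry-forward rule for externally treated lesions, with a sensitivity analysis that counts them as progressed.
- If pulpitis stays as a route to progressed, call the endpoint a composite and report the radiographic part alone.
- State any limit on masking, if the examiner also treated the children or if separation shows on the bitewing.
- State that follow-up visual and SFE scores are not comparable between arms while spacer use differs.

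The sponsor must reconcile the exit and withdrawal thresholds (9.5, Table 14.1.2) and the spacer passages (8.2, 9.1, 9.4.1, 9.5). No position is taken here on which is right.

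**Cost.** Wording in those sections and coding of bitewings already planned. The endpoint itself needs no extra visit or radiograph. The dental examination leaves the primary. Whether spacer use changes depends on how the sponsor reconciles those passages.

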6.4 Study Overview

We propose a randomized, blinded, clinical study of Icon vs. Control (Oral Hygiene Instruction [OHI] and topical fluoridation) as early caries interventions for caries arrest in pediatric populations. 50 non-cavitated early caries lesions, or areas of demineralization, in proximal surfaces of primary molars will be enrolled in this study. Up to 2 early caries lesions may be enrolled per patient, providing the second lesion is in a separate quadrant. Early caries lesions with demineralization seen on occlusal surfaces will be excluded from participation, along with white spot lesions from hypoplasia or fluorosis.

7 Design of the Clinical Investigation

The study will be designed as a controlled, randomized, blinded trial following CONSORT⁴² recommendations as a single center study to investigate the effect of caries infiltration as an alternative treatment option for approximal caries lesions.

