7.2 Participant Selection

Individuals will be selected among the children who come to the Center for Pediatric Dentistry Seattle, Washington, USA for dental treatment. Healthy children between 6 and 13 years old, presenting at least one pair of early carious lesions in primary molars.

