9.3 Randomization

25 non-cavitated early caries lesions will be randomly assigned, using a random numbers table, to study arm 1) the Icon treatment group; and 25 non-cavitated early caries lesions will be randomly assigned, using a random numbers table, to study arm 2) the Control group (OHI and topical fluoridation).

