14.2 Withdrawal / Dropout of Subjects

Table 14.1.2 Withdrawal and drop-out of subjects separated by level, reason and consequences

Level	Cause	Consequence
Lesion	An allocated lesion progresses radiographically into the middle or inner 1/3 of dentin (criteria D2 and D3).	
The lesion is treated invasively by removing the caries and placing a filling.
 
The case is scored as "progressed" and "failure".

	The patient shows signs of reversible or irreversible pulpitis in an allocated tooth.	
The tooth is treated.
 
The case is scored as "progressed" and "failure".

Patient	The patient shows adverse reactions for one of the study materials.	
Counteractive measures are taken.
 
Unwanted effects are documented in CRF and CEF.
 
The patient is scored as "drop out", data will be assigned as "last observation carried

		forward".
	The patient can not be examined (i.e. x-ray during pregnancy)	The patient is scored as "drop out", data will be assigned as "last observation carried forward".
	One or more allocated lesions have been treated by an external dentist.	The patient is scored as "drop out", will be assigned as "last observation carried forward".
	The patient can not be contacted to make appointments.	The patient is scored as "drop out".
	The patient decides to withdraw his informed consent or study participation.	The patient is scored as "drop out".
Study	One or more patient(s) show severe unwanted side effects to treatment.	Individual counteractive measures are taken. The study is halted.
	More than five patients show unwanted side effects to one treatment or material used.	Individual counteractive measures are taken. The study is halted.

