18.4 Report by the sponsor to the National Competent Authorities

Reportable events will be reported at the same time to all National Competent Authorities where the clinical investigation has commenced.

- a SAE which indicates an imminent risk of death, serious injury, or serious illness and that requires prompt remedial action for other patients/subjects, users or other persons or a new finding to it: immediately, but not later than **2 calendar** days after awareness by sponsor of a new reportable event or of new information in relation with an already reported event.
- any other reportable events or a new finding/update to it: immediately, but not later than **7 calendar** days following the date of awareness by the sponsor of the new reportable event or of new information in relation with an already reported event.

19 Early Termination or Suspension of the Investigation

All materials and devices used in this study have been approved by local regulatory bodies and are currently on the market in various parts of the world. Their clinical use in this investigation is according to label. Therefore, early termination or suspension of the investigation due to problems with the restorative materials is not anticipated.

If the investigation is terminated prematurely or suspended, the principal clinical investigator will promptly inform the clinical investigators of the termination or suspension and the reason(s) for this.

The ethics committees will also be informed promptly and provided with the reason(s) for the termination or suspension by the principal clinical investigator.

If the results of Icon or Control failed or is found to be clinically unsatisfactory, the Principal Investigator will provide an alternative treatment (of a different tooth colored restorative such as a composite resin restorative and bonding system, or other direct restorative system, at the discretion of the clinician,) to the subject. The subject will then be discontinued from the study.

20 Publication Policy

The study investigator may present or publish the results of scientific investigation involving this study. Details are described in the study contract section 6 in detail.

21 Administrative Arrangements

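### Section 9.5 removes the whole child when one lesion progresses, so the child's other lesion loses its 24-month reading because of a different tooth, with a bias of undetermined direction

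*Combined protocol and SAP*

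**What the plan says.** **Who leaves, and when.** Protocol section 9.5 defines progression as a change "from E2 to D category according to DMG's criteria", has the child referred for standard care, and continues: "The study participant will no longer participate in the study at this point". Section 19 has a second exit at the level of the child. If Icon or the control treatment fails or is clinically unsatisfactory, another treatment is given and "The subject will then be discontinued from the study". Table 14.1.2 in section 14.2 treats progression as a lesion-level event at a different depth: "An allocated lesion progresses radiographically into the middle or inner 1/3 of dentin (criteria D2 and D3"). There the case is scored as progressed and as a failure, and no exit of the child is stated.

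**Lesions per child.** Section 6.4: "Up to 2 early caries lesions may be enrolled per patient, providing the second lesion is in a separate quadrant". Section 7.2 instead describes children "presenting at least one pair of early carious lesions in primary molars".

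**Unit of randomization.** Section 9.3: "25 non-cavitated early caries lesions will be randomly assigned, using a random numbers table, to study arm 1) the Icon treatment group", with the same number for control. Section 9.4.1 also speaks of randomized lesions. Sections 8.2, 9.1 and 9.4.2 speak of randomized participants. The SAP sizes the trial for matched pairs and tests with Fisher's exact test.

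**Outcome and missing data.** The SAP's primary outcome is the proportion of lesions progressed at 2 years, with visits at 12 and 24 months. Section 11.4.4 says missing data will be at random. "Data of dropouts will be assigned as" last observation carried forward, it adds.

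**The concern.** The outcome is counted per lesion, but the exit rule acts on the child. A sound lesion can therefore go unread at 24 months only because another tooth in the same mouth progressed. This loss is produced by the outcome under study, which does not fit the statement in section 11.4.4. The two arms are expected to progress at very different rates, so the loss need not balance between them. Which arm loses more depends on whether a child's two lesions can be in different arms. How the loss moves the result also depends on whether the unread lesion is carried forward or left out. The documents settle neither point, so the same true difference could be reported as quite different figures.

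**Working it through.** **The plan's own figure.** The plan gives no figure for this loss. The nearest is the SAP's 42 lesions, which reproduces as pairs. Assume 23% and 63% (the SAP's 40-point difference set on its cited 23%). The SD of the paired difference is √(0.23×0.77 + 0.63×0.37) = 0.6405, so the standardized difference is 0.40/0.6405 = 0.625. Then (1.96 + 0.84)²/0.625² ≈ 20.1, giving 21 pairs, or 42 lesions. Enrolling 50 leaves a margin of 8 lesions.

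**Inputs.** From section 4.3.4: progression of Icon lesions is 16% at 1 year and 24% at 2 years, and of control lesions 53% and 62%. The true 2-year difference is 62 − 24 = 38 points.

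**Assumptions, chosen to give an upper range.** Every child has two lesions (25 children, 25 lesions per arm). Every lesion progressed at 12 months triggers exit. There is no within-child correlation.

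**Formulas.** Let h be the chance that the other lesion progressed at 12 months, and p₁, p₂ the arm's 1- and 2-year rates.
- Share of lesions losing the 24-month reading: (1 − p₁)·h
- Recorded progression under carry-forward: L = p₁ + (p₂ − p₁)(1 − h)
- Recorded progression if lost lesions are excluded: L / [1 − (1 − p₁)h]

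**Values of h.**
- One lesion per arm: Icon 0.53, control 0.16.
- Lesions allocated independently 25:25: the two lesions differ in arm with probability 25/49. Icon (25/49)(0.53) + (24/49)(0.16) = 0.349; control (25/49)(0.16) + (24/49)(0.53) = 0.341.
- Child randomized: Icon 0.16, control 0.53.

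**Worked case, one lesion per arm.** Lost: Icon 0.84×0.53 = 44.5%, control 0.47×0.16 = 7.5%. Carry-forward: Icon 0.16 + 0.08×0.47 = 19.8%, control 0.53 + 0.09×0.84 = 60.6%, difference 40.8. Excluded: Icon 0.1976/0.5548 = 35.6%, control 0.6056/0.9248 = 65.5%, difference 29.9.

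| Allocation | Lost, Icon (of 25) | Lost, control (of 25) | Difference, carry-forward | Difference, excluded |
|---|---|---|---|---|
| One lesion per arm | 44.5% (11.1) | 7.5% (1.9) | 40.8 | 29.9 |
| Independent | 29.3% (7.3) | 16.0% (4.0) | 37.7 | 40.2 |
| Child randomized | 13.4% (3.4) | 24.9% (6.2) | 34.5 | 50.0 |

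**Sensitivity to the rates.** With the cited 1-year primary-tooth rates (23% and 62%), the expected losses, Icon versus control, are 11.9 versus 2.2, 8.3 versus 4.0 and 4.4 versus 5.9 lesions. With a within-child correlation of 0.3 they are 10.4 versus 0.7, 6.8 versus 2.4 and 3.1 versus 4.1. The arm that loses more is the same in each allocation.

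**Sensitivity to the number of two-lesion children.** With 10 such children, 20 of the 50 lesions (40%) are exposed, so each h is multiplied by 0.4. The 38 points then read 39.1, 37.9 and 36.6 under carry-forward, and 36.2, 39.0 and 41.9 with exclusion. With no two-lesion children nothing is lost.

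**The case against.** **The effect may be small.** Only two-lesion children are exposed, and their number is not given. Only progression found before the 24-month visit matters, in practice at 12 months. The rates used are for progression in general, while section 9.5 is triggered only by E2 to D, and E1 lesions are also enrolled. Under independent allocation with carry-forward the shift is only 0.3 points. All of this stands, and it is why the figures are labelled an upper range.

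**Table 14.1.2 may already protect the second lesion.** It handles progression per lesion. But it uses another depth, it does not say the child stays in, and sections 9.5 and 19 say the child leaves.

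**The loss could still be called missing at random in the technical sense,** because its trigger is recorded. That helps only if the analysis uses both lesions' 12-month readings. Neither carry-forward nor exclusion does so.

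**A stronger reading is tempting.** A reader might infer that Icon lesions are lost more often, because control lesions progress more, and that this flatters Icon. The documents do not support that as a general statement. It needs a child's lesions to be allocated separately or to opposite arms (sections 9.3 and 9.4.1). If children are randomized (sections 8.2, 9.1 and 9.4.2), control loses more. Pairing across arms is only hinted at by section 7.2 and the SAP's matched-pairs sizing. Even with one lesion per arm, the result favours Icon under carry-forward (40.8) and goes against it under exclusion (29.9). Carry-forward is itself not assured, since Table 14.1.2 does not list progression among the child-level dropout rows.

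**Conclusion.** The point holds in this form. Followed literally, section 9.5 costs an unprogressed second lesion its 24-month reading because of another tooth. That loss depends on outcome and can be unequal between arms. Its direction and size cannot be fixed from the documents, because the unit of randomization is contradictory and the scoring of the other lesion is not clearly stated. At the upper range, a true 38 points can be reported as anything from 29.9 to 50.0. Under carry-forward alone the range is 34.5 to 40.8. Carry-forward shifts fall in proportion to the share of lesions in two-lesion children; exclusion shifts also fall, though not strictly in proportion. Both fall further because the trigger is only E2 to D, whose 12-month rate is not given. This should be corrected, but it does not by itself show that the trial favours either arm.

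**What to change.** 1. In section 9.5, make exit from outcome follow-up apply to the lesion scored as progressed. Keep the child's other lesion in the scheduled 12- and 24-month outcome assessments, and score it on its own reading.
2. Reconcile section 9.5, Table 14.1.2 and section 19 on who exits and at what depth. Changing section 9.5 alone would leave the child-level exit in section 19. The choice of depth is for the investigators, and this review does not make it.
3. State one unit of randomization across sections 8.2, 9.1, 9.3 and 9.4, and use an analysis that allows for two lesions from one child.
4. State how a lesion is scored if its 24-month reading is still missing.

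Referral for care is unaffected. The cost is a few sentences of text, plus attendance by retained children at follow-up assessments already planned: bitewings (standard care), visual exam, SFE imaging, and spacers where planned.
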